8.7 Validation of Statistical Analyses

Programs will be developed and maintained, and output will be verified in accordance with current risk-based quality control procedures.

Tables, figures, and listings will be produced with validated standard macro programs where standard macros can produce the specified outputs.

The production environment for statistical analyses consists of Amgen-supported versions of statistical analysis software; for example, the SAS System version 9.4 or later.

9. Statistical Methods of Analysis

9.1 General Considerations

Summary statistics will be computed by treatment group and visit. For continuous endpoints, the following descriptive statistics will be computed: number of observations, means, medians, standard deviations, standard errors, first and third quartiles, minimums and maximums, and 2-sided 95% confidence intervals (CIs) of the means (CIs will be provided for efficacy endpoints only). For categorical endpoints, the summaries will contain the number and percentage of subjects in each category.

For the primary and secondary endpoints, the primary analysis method utilizing a repeated measures linear mixed effects model will include all observed data regardless of treatment adherence.

A sequential testing procedure will be used to maintain the family-wise type 1 error $\alpha = 0.05$ between the primary and secondary endpoints following the prespecified order below. An endpoint will only be tested for statistical significance if the endpoint tested in the previous step is statistically significant at 2-sided significance level of 0.05.

- 1. Primary endpoint: change from baseline in mean monthly hours of at least moderate headache pain intensity over months 1, 2, and 3
- Secondary endpoints: change from baseline in mean monthly function over months 1, 2, and 3, as measured by the MFIQ using the Hochberg procedure
 - Impact on physical functioning

- Impact on usual activities
- Impact on emotional functioning
- Impact on social functioning
- 3. Secondary endpoint: change from baseline in mean monthly average duration of at least moderate pain intensity **in** migraine attack**s** over months 1, 2, and 3
- 4. Secondary endpoint: change from baseline in mean monthly peak migraine pain intensity over months 1, 2, and 3, as assessed by the 11-point NRS

9.2 Subject Accountability

The disposition of all randomized (enrolled) subjects will be tabulated by randomized treatment group. The summary will include the number of subjects who are randomized, the number and percent of subjects who receive/never receive double-blind IP, who complete double blind IP, discontinue double-blind IP and reasons for discontinuing, who complete the study, and who withdraw prematurely from the study before completion of the study and their reasons for withdrawal. Summary of subjects who discontinue investigational product/study due to COVID-19 control measures will be included.

9.3 Important Protocol Deviations

Important Protocol Deviations (IPDs) categories are defined by the study team before the first subject's initial visit and updated during the IPD reviews throughout the study prior to database lock. These definitions of IPD categories, subcategory codes, and descriptions will be used during the course of the study. Eligibility deviations are defined in the protocol. IPDs will be summarized and listed by randomized treatment group.

Protocol Deviations (PDs) related to COVID-19 control measures will be summarized separately.

9.4 Demographic and Baseline Characteristics

Subject demographic and baseline characteristics will be summarized using descriptive statistics by randomized treatment group and overall study population using FAS. If multiple races have been reported for a subject, the subject will be categorized as multiple races as well as by combination of races.

At baseline, the following demographic and baseline characteristics will be summarized:

- Age
- Sex
- Ethnicity
- Race
- Height (cm)

- Weight (kg)
- Body mass index (BMI, kg/m²)
- Targeted neurological disease diagnosis at baseline
- Disease duration of migraine with or without aura
- Age at onset of migraine
- Summary of prior migraine preventive medication and reasons for discontinuation
- Acute headache medication use during baseline period:
 - a) Migraine-specific
 - b) Non migraine-specific
- Monthly migraine days during baseline period
- Monthly headache days during baseline period
- Monthly hours of at least moderate headache pain intensity
- Monthly average duration of at least moderate pain intensity per migraine attack
- Monthly average peak migraine pain intensity
- Monthly total migraine freedom days
- Monthly hours of at least moderate pain intensity for triptan-treated migraine attacks
- MFIQ domain scores of function (physical, usual activities, social, and emotional)
- HIT-6 total score
- MTS
- MSSS total score
- PGI-S score
- MIBS-4 total score
- PCS total score

9.5 Efficacy Analyses

The primary and secondary efficacy analyses will utilize the M-DBTP EAS and the exploratory efficacy analyses will utilize the E-DBTP EAS. Subjects will be analyzed according to their randomized treatment group regardless of the actual treatment received during the study.

Detailed efficacy analysis methods and covariates included in the models are summarized in the table below.

Endpoint	Primary Summary and Analysis Method
Change from baseline in mean monthly hours of at least moderate headache pain intensity over months 1, 2, and 3	 Summary statistics by visit using observed data at each visit and the calculated mean monthly hours of headache pain over months 1, 2, and 3
	2. Least squares means from a linear mixed effect model including treatment group, scheduled visit, interaction of treatment and scheduled visit and baseline value using observed data
	 Estimate treatment difference (AMG 334 – Placebo) from the model in #2.

Table 9-1. Primary Efficacy Endpoint Summary Table

Table 9-2. Secondary Efficacy Endpoint Summary Table

Т

Endpoint	Primary Summary and Analysis Method
Change from baseline in mean monthly function as measured by the Migraine Functional Impact Questionnaire (MFIQ) over months	 Summary statistics by visit using observed data at each visit, and the calculated mean monthly values over months 1, 2 and 3
1, 2, and 3; Change from baseline in mean	 Least squares means from a linear mixed effect model including treatment group, scheduled visit, interaction of treatment and scheduled visit and baseline value using observed data
monthly average duration of at least moderate pain intensity in migraine attack s over months 1, 2, and 3;	 Estimate treatment difference (AMG 334 – Placebo) from the model in #2
Change from baseline in mean monthly peak migraine pain intensity as assessed by the 11-point Numeric Rating Scale (NRS) over months 1, 2, and 3	

Endpoint	Primary Summary and Analysis Method
Change from baseline in mean MMD over months 1, 2, and 3 ^a	 Summary statistics by visit using observed data at each visit and the calculated mean monthly migraine day over months 1, 2, and 3 Least squares means from a linear mixed effect model including treatment group, scheduled visit, interaction of treatment and scheduled visit and baseline value using observed data Estimate treatment difference (AMG 334 – Placebo) from the model in #2.
Change from baseline in pain catastrophizing as measured by the Pain Catastrophizing Scale (PCS) at month 3 ^b	 Summary statistics using observed data at week 12 Analysis of covariance (ANCOVA) model including treatment group and baseline value using observed data Estimate treatment difference (AMG 334 – Placebo) using the model in #2.
Achievement of no or mild interictal burden as measured by the MIBS-4 at assessment time points ^c	 Summary statistics using observed data at the specific month Logistic regression model including treatment group and baseline value will be used after subjects with missing outcome data are imputed as non-responders (NRI)

Table 9-3. Exploratory Efficacy Endpoint Summary Table

Endpoint	Primary Summary and Analysis Method	
Achievement of pain freedom at 2 hours post-triptan dose for the first attack at month 4 ^d	Summary sta assessment f	itistics using observed data at the time points
	group will be	ession model including treatment used after subjects with missing ment are imputed as non-responders
Use of migraine rescue medication within 24 hours post-triptan dose for the first attack at month 4	Summary sta assessment	atistics using observed data at the time points
		ression model including treatment observed data
^a The same analyses methods will be applie	the endpoints:	

The same analyses methods will be applied to the endpoints:

Change from baseline in mean monthly hours of at least moderate pain intensity for qualifying oral triptan-treated migraine attacks over months 1, 2, and 3

Change from baseline in mean average duration of at least moderate pain intensity for qualifying oral triptan-treated migraine attacks occurring over months 1, 2, and 3

Change from baseline in Migraine Symptom Severity Score (MSSS) total score at assessment time points Change from baseline in mean monthly total migraine freedom days over months 1, 2, and 3

Change from baseline in Migraine Interictal Burden Scale (MIBS-4) total score at assessment time points (the model will include data at month 1-4)

Change from baseline in headache impact scores as measured by the Headache Impact Test (HIT-6) total score at assessment time points

Change from baseline in physical function domain score as measured by MFIQ at assessment time points Change from baseline in usual activities domain score as measured by MFIQ at assessment time points

Change from baseline in social function domain as measured by MFIQ at assessment time points Change from baseline in emotional function domain score as measured by MFIQ at assessment time points

Change from baseline in overall impact on usual activities global item score as measured by MFIQ at assessment time points

Change from baseline in mean monthly average duration of at least moderate pain intensity per migraine attack in months with at least 1 migraine attack

Change from baseline in mean monthly peak migraine pain intensity as assessed by the 11-point Numeric Rating Scale (NRS) in months with at least 1 migraine attack

^b The same analyses methods will be applied to the endpoints: Change in Patient Global Impression of Severity (PGI-S) total score at month 3

^c The same analyses methods will be applied to the endpoints: Change from baseline in the most troublesome symptom (MTS) at month 3

 ^d The same analyses methods will be applied to the endpoints: Achievement of pain freedom at 30 and 60 minutes post-triptan dose for the first attack at month 4 Achievement of pain relief at 2 hours post-triptan dose for the first attack at month 4 Achievement of freedom from the most bothersome symptom at 30, 60, and 120 minutes post-triptan dose for the first attack at month 4 Achievement of relief from the most bothersome symptom at 30, 60, and 120 minutes post-triptan dose for the first attack at month 4 Achievement of 24-hour sustained pain freedom post-triptan dose for the first attack at month 4 Migraine recurrence during 24 hours post-triptan dose for the first attack at month 4

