Urine pregnancy test (females of childbearing potential only)	Х			X				X	Additional on-treatment pregnancy testing may be performed at the investigator's discretion if there is suspicion that a female subject is pregnant or per local laws and regulations
Urine drug testing	Х								Urine drug testing can be done as needed throughout the study per investigator discretion.
BIOMARKER AND PHARMACOGENETIC ASSESSMENTS (OPTIONAL)									
Biomarker development, blood				Х					
Pharmacogenetic studies ^f				Х					

Table 1-1. Schedule of Activities

Footnotes defined on the last page of the table.

Page 3 of 4

	Screening Period			Double blind Treatment Period (weeks) ^c						
	Initial	Run-in ^a	Baseline Period ^b D -28 to D -1 (+7 days)			Notes				
PROCEDURE	(up to 3 weeks, 21 days)	(2 weeks, 14 days [+4 days])		Day 1 (± 3 days)	W 4 (± 3 days)	W 8 (± 3 days)	W 12 ^d (± 3 days)	W 16/ EOS ^d (± 3 days)		
CLINICAL OUTCOME ASSESSI	MENTS									
Episode eDiary		Xa						Xa		
Daily eDiary			Daily		Da	aily				
MFIQ				Х	Х	Х	Х			
MSSS				Х	Х	Х	Х			
Change in most troublesome symptom				Х			Х			
PGI-S				Х			Х			
MIBS-4				Х	Х	Х	Х	Х		
HIT-6				Х	Х	Х	Х			
PCS				Х			Х			
STUDY-RELATED DEVICE ASS	GNMENT									
Assign eDiary device		Х								
STUDY TREATMENT										
Amgen investigational product				X	Х	X	Х		Site staff will administer the dose as the last procedure of the visit.	

Table 1-1. Schedule of Activities

Page 4 of 4

D = day; eDiary = electronic diary; EOS = End of Study; HIT-6 = Headache Impact Test; MFIQ = Migraine Functional Impact Questionnaire; MIBS-4 = Migraine Interictal Burden Scale; MSSS = Migraine Symptom Severity Score; PCS = Pain Catastrophizing Scale; PGI-S = Patient Global Impression of Severity; PHQ-9 = Patient Health Questionnaire; W = Week

^a The run-in period ends when at the end of the period the subject does not meet inclusion criterion 108 or enters the baseline period (see Section 8.1.2).

- ^b The baseline period starts when the subject has met all initial eligibility criteria, has completed the run-in period, and has met inclusion criterion 108. The baseline period ends when the subject does not meet inclusion criterion 109 through to 112 and is screen-failed or when subject meets all eligibility criteria and is enrolled and randomized. The total duration of the baseline period must be at least 28 days and no more than 35 days (see Section 8.1.3).

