8.1.4 Treatment Period

Visits will occur per the Schedule of Activities (Table 1-1). The date of the first dose of investigational product is defined as day 1. All subsequent doses and study visits will be scheduled based on the day 1 date. Study visits after day 1 may be completed within ± 3 days of the scheduled visit. All study procedures for a given study visit are to be completed on the same day. Investigational product is to be administered Q4W as the last procedure during each visit that it is required.

Subjects who discontinue investigational product are encouraged to remain in the study and complete all remaining procedures and study visits.

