8.1.5 End of Study

The end-of-study visit occurs at week 16 or 4 weeks after last dose of investigational product for subjects who discontinue the study. If a subject discontinues treatment or the study prior to week 12, the week 12 assessments should be conducted for their early termination visit. Assessments will be performed at the end-of-study visit as per Schedule of Activities (Table 1-1).

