6.2 M-DBTP Efficacy Analyses Set

The respective efficacy analysis set for each efficacy endpoint consists of a subset of subjects from full analysis set who receive at least 1 dose of investigational product and have **observed monthly hours of at least moderate headache pain intensity at baseline and at least 1 measurement during M-DBTP**. Subjects will be analyzed according to their randomized treatment, regardless of treatment received. Primary analysis of the efficacy endpoints during M-DBTP will utilize this efficacy analysis set.

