6.3 E-DBTP Efficacy Analysis Set

The E-DBTP efficacy analysis set consists of a subset of subjects from full analysis set who receive week 12 dose. Subjects will be analyzed according to their randomized treatment, regardless of treatment received. Analysis of exploratory efficacy endpoints during E-DBTP will utilize this efficacy analysis set.

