9.5.2 M-DBTP Analyses of Exploratory Efficacy Endpoints

For exploratory efficacy endpoints during the M-DBTP, summary statistics and primary analysis method will be conduct in the same way as that for the primary and secondary endpoints.

The continuous exploratory efficacy endpoints at each assessment time point or over months 1, 2, and 3 of the 3-month M-DBTP will be analyzed using the

linear mixed effects model that includes treatment group, baseline values, scheduled visit, and the interaction of treatment and scheduled visit without any imputation for missing data.

The efficacy endpoints for PCS total score and PGI-S score will be analyzed using analysis of covariance model including treatment and baseline value as covariates. The efficacy endpoints for **MTS** (achievement of "Very Much Improved" or "Much Improved") and the MIBS (achievement of no or mild interictal burden) will be analyzed using logistic regression model with missing data imputed using NRI **up to End of Study Date**. No sensitivity analyses will be performed for the exploratory endpoints.

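### SAP 9.5 sends every exploratory analysis to the week-12-dose set, contradicting SAP 6.2 and 6.3 for the 18 exploratory endpoints listed under months 1-3

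*SAP*

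**What the plan says.** SAP 9.5, which introduces the efficacy tables, states: "The primary and secondary efficacy analyses will utilize the M-DBTP EAS and the exploratory efficacy analyses will utilize the E-DBTP EAS". It does not limit the second half to month 4.

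The sections that define the sets divide them by period:

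- SAP 6.2, on the M-DBTP set: "Primary analysis of the efficacy endpoints during M-DBTP will utilize this efficacy analysis set".
- SAP 6.3, membership: "The E-DBTP efficacy analysis set consists of a subset of subjects from full analysis set who receive week 12 dose".
- SAP 6.3, scope: "Analysis of exploratory efficacy endpoints during E-DBTP will utilize this efficacy analysis set".

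SAP 9.5.2 covers the exploratory endpoints of the main period. It says that the "primary analysis method will be conduct in the same way as that for the primary and secondary endpoints" and names no analysis set. SAP 10 records that the protocol's single efficacy set was split in two to suit the target population of each endpoint class, which is compatible with either reading.

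**The concern.** For an exploratory endpoint measured in months 1-3, SAP 9.5 points to one population and SAP 6.2 and 6.3 to another. Two programmers following different sections would build different populations for the same table.

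The literal 9.5 reading is also statistically poor. It makes membership depend on an event after randomisation that follows the outcome. It removes observed data from treated subjects who stopped drug but stayed, although the protocol asks for those data. Section 8.1.4: "Subjects who discontinue investigational product are encouraged to remain in the study and complete all remaining procedures and study visits". Section 8.1.5: "If a subject discontinues treatment or the study prior to week 12, the week 12 assessments should be conducted for their early termination visit". A subject who stops treatment before week 12 does not receive the week 12 dose.

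For MIBS-4 response and the most troublesome symptom, missing outcomes are imputed as non-response. Under literal 9.5, subjects without that dose would leave the denominator instead of counting as non-responders.

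**Working it through.** The plan states no figure on this point to reproduce. The check is a comparison of passages, a count, and a range.

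**1. Is there a reading that reconciles the sections?** SAP 6.2 speaks of the primary analysis of main-period endpoints, which might be taken to mean primary endpoints only. But SAP 9.5.2 uses the same term for the exploratory endpoints of that period and rules out sensitivity analyses for them. So 6.2 covers them, and 9.5 conflicts with it directly. It also conflicts with the scope sentence of 6.3. SAP 9.5.2 conflicts with 9.5 only by implication.

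**2. Which endpoints are affected?** Exploratory endpoints listed under months 1-3 in protocol Section 3 and SAP 2.1:

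- Diary-derived: hours in triptan-treated attacks; average duration in triptan-treated attacks; migraine freedom days; MMD; duration in months with an attack; peak pain in months with an attack. Total 6.
- Questionnaire: MSSS; most troublesome symptom; PGI-S; MIBS-4 total; MIBS-4 response; HIT-6; four MFIQ domains; MFIQ global item; PCS. Total 12.

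6 + 12 = 18. MIBS-4 is also collected at week 16. Setting aside its two endpoints leaves 18 - 2 = 16 confined to months 1-3.

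**3. Does the dose come after the outcome?**

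- Diary: in SAP Table 5-1 the month 3 interval ends the day before the week 12 dose. If that dose date is missing, a footnote supplies a 28-day interval, so the derivation expects month 3 data from subjects without the dose.
- Questionnaires: the Schedule of Activities notes: "Site staff will administer the dose as the last procedure of the visit". The week 12 questionnaires therefore precede it.

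**4. What would be reported twice?** SAP 9.5.1 tabulates treatment differences by visit for the four MFIQ secondary endpoints in the M-DBTP set. Footnote a of Table 9-3 repeats the same domains by visit with the same model terms. 4 domains x 3 visits (weeks 4, 8, 12) = 12 contrasts, which under literal 9.5 come from two populations. The duration and peak-pain versions limited to months with an attack would likewise leave the population of the secondary endpoints they support.

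**5. How many subjects?** The documents give no missed-dose rate. The nearest figure is the planned 10% dropout: 576 x 0.10 = 57.6, about 58. It is not the same quantity, because some dropouts leave after week 12 and subjects who stop drug but stay are not dropouts. For an assumed range:

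- 5%: 576 x 0.05 = 28.8, about 29 outside the set
- 15%: 576 x 0.15 = 86.4, about 86 outside the set

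These counts are of randomised subjects. The net loss is smaller for endpoints analysed on observed data, since a subject with no usable value is lost under either set. For PCS and PGI-S, only a value in days 72-99 counts (Table 5-5).

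**6. How much bias?** The documents support no figure. As illustration only, suppose excluded subjects all have data and do g SD worse than those retained, with fractions qP (placebo) and qE (erenumab) excluded. The shift in the treatment difference is g x (qP - qE), understating benefit when qP is larger. With g = 0.5 (assumed):

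- 10% in each arm: 0.5 x 0 = 0 SD
- 12% placebo, 8% erenumab: 0.5 x 0.04 = 0.02 SD
- 15% placebo, 5% erenumab: 0.5 x 0.10 = 0.05 SD

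**7. What stays open if 9.5 is read by period?** Footnote a of Table 9-3 fits one MIBS-4 total-score model to months 1-4. SAP 6.2 and 6.3 then place its months 1-3 and month 4 estimates in different sets.

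**The case against.** The definitions in 6.2 and 6.3 both assign sets by period, and Sections 9.5.2 and 9.5.3 are divided the same way. A careful programmer would probably read 9.5 as loose wording. Only exploratory endpoints are involved. That is right, and it keeps the priority low to moderate. It does not say which text governs, and 9.5 is the section that heads the analysis tables.

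Other points that stand:

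- The M-DBTP set also selects after randomisation: at least one dose and at least one main-period measurement. The contrast is between weaker and stronger selection.
- The two sets are not nested, because the E-DBTP set has no diary condition. This matters little: inclusion criterion 111 requires 80% baseline diary compliance (0.80 x 28 = 22.4 days, against a 14-day threshold).
- An early termination visit before day 72 gives no usable PCS or PGI-S value under either set. The protocol 8.1.5 argument has more force for instruments with earlier visit windows (Tables 5-3 and 5-4).
- Whether MIBS-4 response is analysed at week 16 is ambiguous. The scale is collected then, but the month 4 list names only the total score.
- Which set the MIBS-4 model should use is a judgement. That one set must be named is not.

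**Conclusion.** The contradiction is real, and SAP 9.5 is wrong as written. It covers 18 exploratory endpoints and 12 potentially duplicated MFIQ contrasts. Those counts come straight from the documents; the 29 to 86 subjects rest on the assumed 5-15% missed-dose rate, and the bias illustration is assumption throughout. By-period assignment is the likely intent. The 9.5 sentence leaves the primary and secondary endpoints, the testing sequence and type 1 error alone. It should be corrected because the population for an analysis ought to be fixed before unblinding, and because the MIBS-4 gap remains even on the charitable reading.

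**What to change.** 1. Reword SAP 9.5: primary, secondary and months 1-3 exploratory endpoints use the M-DBTP set; the month 4 triptan-attack endpoints use the E-DBTP set.
2. Name one set for the MIBS-4 model over months 1-4. The M-DBTP set fits, since one model produces all the estimates. Add the matching exception to 6.3, because the SAP lists MIBS-4 at month 4 as an E-DBTP endpoint. State the set for MIBS-4 response at week 16 if that is to be analysed.
3. Separate and minor: SAP 6.2 calls its set specific to each endpoint, yet appears to define membership by monthly-hours data alone, which could drop MFIQ data for diary reasons. It could be aligned with protocol 9.3.1.2, which asks for a baseline and at least one later value of the endpoint analysed. SAP 10 notes the change of sets but does not mention this criterion.

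The cost is a few sentences in 9.5 and 6.3, optionally 6.2 and the line in SAP 10, plus matching population flags. No new data collection is needed.
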